In the COVID-19 study, no increase in transaminases was seen at either upamostat dose level as compared to placebo. International Normalized Ratio (INR) or activated partial thromboplastin time (aPTT) were often mildly abnormal at baseline in patients in the COVID-19 study. On-study, 25% of placebo patients, 50% of upamostat 200 mg recipients and 62% of upamostat 400 mg recipients developed increases in either INR or aPTT of at least one grade per National Cancer Institute (NCI) Common Terminology Criteria for Adverse Events (CTCAE) v 5.0. Almost all increases were Grade 1; no clinical bleeding was noted.

C.3.4.1.2 Steps Taken to Minimize Risks

1. Risk to participants in this trial may be minimized by compliance with the eligibility criteria and study procedures, close clinical monitoring, as well as periodic review of all safety data by an independent data monitoring committee
2. Because upamostat may inhibit CYP3A4, patients receiving anticoagulants metabolized by CYP3A4 (warfarin, apixaban [Eliquis], or rivaroxaban [Xarelto]) may not be entered into the study, nor may these medications be started while a patient is receiving upamostat.

C 3.4.3 Assessment of Potential Risks and Benefits

This study involves potential risks to and potential health benefits for the participant. Potential benefits, along with anticipated vital knowledge the trial is likely to generate, suggest that benefits of the study outweigh the risks.

C 4 OBJECTIVES AND ENDPOINTS

C 4.1 Early Treatment

In addition to those listed in the MP, the following objectives and endpoints will be included:

	Objectives	Endpoints

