The administration of IP to any participant may be stopped or paused for any SAE, clinically significant AE, severe lab abnormality or any medical condition that may indicate to the Investigators that IP continuation is not in the best interest of the participant. In addition, a subject in the clinical trial may discontinue study drug at their request for any reason. Every effort should be made to encourage subjects to remain in the study for the duration of their planned outcome assessments. Unless the subject withdraws the consent, those who discontinue study drug early will remain in the study. The reason for subject discontinuation will be documented in the case report form.

For an individual participant, the 14-day course of IP can be interrupted or stopped if there is a suspected drug-related event suggestive of QTc interval prolongation, anticoagulant effect, elevated liver enzymes or other, as per investigator or medical monitor discretion if it is deemed to be in the participant's best interest. All participants will receive baseline chemistry, liver enzyme, and coagulation studies as well as a baseline ECG.

The individual pause and stopping criteria will include (but not be limited to) the following:

- The subject worsens and requires treatment for worsening COVID-19 as recommended by the NIH COVID-19 Treatment Guidelines. Upamostat administration will be discontinued. All other study activities will continue, participant will not be withdrawn from the study.
- The subject worsens and requires hospitalization for worsening COVID-19. Upamostat administration will be discontinued. All other study activities will continue, participant will not be withdrawn from the study.
- QTc Interval: QTc increase >60 msec over baseline: repeat ECG within 48 hours and if >60 msec increase over baseline persists, IP will be discontinued. Participant will continue to be participate in follow up visits and, if necessary, until resolution or stabilization of the event.

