- INR, PTT: increase over baseline > 2 Grades (per NIH DAIDS Table for Grading the Severity of Adult and Pediatric Adverse Events (DAIDS AE Grading Table) corrected Version 2.1, July 2017): pause therapy. Repeat INR and PTT within 48 hours of initial awareness of the abnormal laboratory value. If repeat testing \leq 2 Grades above baseline, may resume therapy until total of 14 days from start; missed days will not be made up. If repeat testing > 2 Grades above baseline, IP will be discontinued. Participant will continue to be participate in follow up visits and, if necessary, until resolution or stabilization of the event.
 - If increase over baseline 1 Grade: no additional follow up
 - If increase over baseline 2 Grades: In addition to scheduled PTT/INR testing on Day 3 and Day 14, participant will have coagulation testing on Day 28. If either PTT or INR is increased by \geq 1 Grade at Day 28, repeat testing will be performed at Week 8. Additionally, participant will be questioned at Day 7, Day 10, Day 14 visits, and

twice weekly from Day 14 until resolution of the coagulation abnormality to ≤ 1 Grade above baseline or Week 8 (whichever comes first), regarding bleeding, bruising or petechiae.

- Transaminases, bilirubin: increase over baseline >1 Grade above baseline: pause therapy. Repeat transaminase and bilirubin levels within 48 hours of initial awareness of the abnormal laboratory value. If repeat testing ≤ 1 Grade above baseline, may resume therapy until total of 14 days from start; missed days will not be made up. If repeat testing >1 Grade above baseline, IP will be discontinued. Participant will continue to be participate in follow up visits and, if necessary, until resolution or stabilization of the event.

C 12.2 Study and/or PSA Pause and Stopping Criteria

In addition to those listed in the Master Protocol, the study pause criteria listed in Table 1 will apply.

Table 1 Product Specific Criteria for Study Pause

Parameter	Investigational Products Related Adverse Events (AEs)	Action
Prolonged QTc Interval	QTc ^a >500 msec OR QTc ^a >60 msec above baseline on repeat ECG within 48 hours	Prompt reporting (within 24 hours of observation or report) Consider pause of the PSA PSRT to monitor for trend
ALT (SGPT), ALP (SGOT), or Total Bilirubin, High	> 1 Grade ^c increase in verified ^d abnormal AST, ALT, and total bilirubin in >2 patients	Prompt reporting (within 24 hours of observation or report) Consider pause of the PSA PSRT to Monitor for trend

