PT, PTT, or INR, High (Not on anticoagulation therapy)	> 2 Grade increase in verified PT, PTT or INR >2 patients	Prompt reporting (within 24 hours of observation or report) Consider pause of the PSA PSRT to Monitor for trend

a Corrected QT may be calculated using any standardized formula or automated interpretation. The same methodology for calculating the QT interval should be applied throughout the participants enrollment in the study

c Per NIH DAIDS Table for Grading the Severity of Adult and Pediatric Adverse Events (DAIDS AE Grading Table) corrected Version 2.1, July 2017

d Verified definition: If no evidence of disease is present other than the abnormal laboratory value, the test must be repeated at least one time in order to be considered “verified”. The verification period will be a maximum of 48 hours after initial awareness of the abnormal laboratory value. When signs and symptoms are present, repeat test WILL NOT be needed

C 13 STATISTICAL CONSIDERATIONS

C13.1 Statistical Hypotheses

The primary hypothesis is that early treatment with upamostat among outpatients infected with SARS-CoV-2 can shorten time to sustained alleviation or resolution of Targeted COVID-19 symptoms (time to resolution) as compared to standard treatment.

The general statistical approach will compare outcomes among participants randomized to receive the active agent, upamostat, to outcomes among participants who were eligible to have been randomized to upamostat but who were randomized instead to any of the placebo arms enrolling at that time. This ensures that the comparison is limited to concurrently randomized participants eligible to receive upamostat.

C 13.4 Primary Endpoint/Estimand Analysis

The primary objective is to estimate the relative time to sustained alleviation or resolution of symptomatic COVID-19 infection for a participant that receives upamostat compared to a participant that does not receive upamostat.

The estimand of interest is the hazard ratio of a participant that has symptomatic COVID-19 with standard of care background therapy when starting treatment with upamostat compared to no upamostat. A hazard ratio greater than 1 indicates a shorter time to resolution of symptomatic COVID-19 infection.

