5.2.6. Adverse events

An adverse event is any untoward medical occurrence associated with the use of an intervention in humans, regardless of whether the event is considered intervention-related or not. All adverse events that occur from the first dose of study medication through Week 12 after enrollment must be recorded.

AEs will be coded using MedDRA, version 24.0 or higher; AE severities will be graded using the Grading the Severity of Adult and Pediatric Adverse Events (DAIDS AE Grading Table), corrected Version 2.1, July 2017.

A treatment-emergent adverse event is defined as any event not present prior to the initiation of the IP or any event already present that worsens in either intensity or frequency following exposure to the IP.

An adverse event (AE) or suspected adverse reaction is considered "serious" if, in the view of either the investigator, medical monitor, or sponsor, it results in any of the following outcomes:

- Death
- A life-threatening adverse event
- Inpatient hospitalization or prolongation of existing hospitalization
- A persistent or significant incapacity or substantial disruption of the ability to conduct normal life functions
- A congenital anomaly/birth defect
- Important medical events that may not result in death, be life-threatening, or require hospitalization may be considered serious when, based upon appropriate medical judgment, they may jeopardize the participant and may require medical or surgical intervention to prevent one of the outcomes listed in this definition

Adverse events can be classified as/by:

- Investigational Product-related or not Investigational Product-related.
 - Relationships reported as definitely, probably, or possibly related are considered related to IP;
 - Relationships reported as unlikely or unrelated are considered not related to IP.
- Severity of Event

For AE not included in the protocol-defined grading system, the following guidelines will be used to describe severity:

- Grade 1 (Mild) – Mild symptoms causing no or minimal interference with usual social & functional activities with intervention not indicated.
- Grade 2 (Moderate) – Moderate symptoms causing greater than minimal interference with usual social & functional activities with intervention indicated
- Grade 3 (Severe) – Severe symptoms causing inability to perform usual social & functional activities with intervention or hospitalization indicated.

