- Grade 4 (Life-threatening) – Potentially life-threatening symptoms causing inability to perform basic self-care functions with intervention indicated to prevent permanent impairment, persistent disability
- Grade 5 (Death)

Safety analyses will include

- Incidence of Serious Adverse Events
- Adverse Events
- Adverse Events \geq Grade 3
- IP discontinuation due to AE
- All-cause IP discontinuation
- Hospitalization due to any adverse events

The number and percentage of participants with AEs will be summarized for each treatment group. Overall treatment group differences may be compared using Chi-square tests or Fisher's exact tests.

Serious AE and hypersensitivity reactions will also be summarized. The counts and proportion of participants experiencing these events will be reported for each treatment arm. Treatment groups may be compared by Chi-square tests or Fisher's exact tests.

Permanent discontinuations or interruptions of upamostat due to AEs will be listed. The count and proportion of discontinuations of the study drug due to AEs will be reported.

Categorical safety measures (e.g. hospitalization) will be summarized with counts and proportions of participants and may be compared by treatment using either a Chi-square test or a Fisher's exact test.

All AE will be summarized by worst DAIDS grade and presented by System Organ Class (SOC), Preferred Term (PT), and treatment group, as follows.

- All AE
- All Related AE
- All AE leading to study drug discontinuation
- All SAE

All AE data will be provided in listings. A listing of any on-study deaths will be presented.

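### The mandatory INR/PTT pause trigger in C 12.1, and its Table 1 counterpart, count only grades above the participant's own baseline, so they become harder to reach, and then unreachable, as baseline coagulation worsens

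*Protocol*

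**What the plan says.** **Individual rule (Protocol Appendix C, C 12.1).** Study drug is paused at "INR, PTT: increase over baseline > 2 Grades", graded by the DAIDS table, and the tests are repeated within 48 hours. "If repeat testing > 2 Grades above baseline, IP will be discontinued". The resume clause is the mirror image: it covers a participant whose repeat is at most "2 Grades above baseline, may resume therapy until total of 14 days from start; missed days will not be made up". A one-grade rise needs no extra follow-up. For a rise of exactly two grades no pause is stated. That branch adds a Day 28 coagulation test, a Week 8 test if Day 28 is still at least one grade up, and repeated questions about bleeding, bruising and petechiae.

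**Study-level rule (C 12.2, Table 1).** The coagulation row reads "> 2 Grade increase in verified PT, PTT or INR >2 patients". It leads to prompt reporting, consideration of a pause of the product-specific arm, and monitoring for trend.

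**Wider wording in C 12.1.** The section opens by saying that study drug "may be stopped or paused for any SAE, clinically significant AE, severe lab abnormality", among other grounds. Its second paragraph allows interruption or stopping, at investigator or medical monitor discretion, for a suspected drug-related anticoagulant effect. The listed criteria are stated not to be exhaustive.

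**Baseline status.** C 3.4.1.1 reports that INR or aPTT "were often mildly abnormal at baseline in patients in the COVID-19 study". C 6.2 excludes users of named anticoagulants but sets no INR/PTT limit. Coagulation is not among the screening assessments in C 9.2.3, and C 9.4.2 lists the Day 0 coagulation sample after Step 2 randomization.

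**Reporting (SAP 5.2.8).** aPTT and INR are summarized as observed values and changes from baseline by arm and visit, with listings that flag out-of-range values. No table by grade or by baseline grade is planned.

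**The concern.** A rule defined only as a rise from the participant's own baseline, on a scale with a fixed top, has less room to operate the higher the participant starts. Coagulation prolongation is the dose-ordered laboratory effect of this drug: C 3.4.1.1 gives INR or aPTT rises of at least one grade in 25% on placebo, 50% at 200 mg and 62% at 400 mg (C 5.4 gives 65% for the 400 mg group). The one mandatory numeric safeguard for that effect therefore weakens in participants whose coagulation is already abnormal at entry. Because Table 1 uses the same count, the study-level signal would leave out the same people. Mean changes by visit, as planned in the SAP, would not show it.

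**Working it through.** The documents give no figure that depends on this rule, so there is nothing to reproduce. The check is an enumeration.

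**Inputs.** Trigger: on-study grade minus baseline grade greater than 2 (C 12.1; same count in Table 1). Comparison rule: transaminases and bilirubin, greater than 1 (C 12.1). Top laboratory grade: taken as 4. This is an assumption; SAP 5.2.6 has a general scale in which Grade 4 is life-threatening and Grade 5 is death, but that scale is for events outside the protocol's grading table.

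**Formula.** Grades are integers, so the lowest grade that triggers is baseline + 3 for INR/PTT and baseline + 2 for transaminases and bilirubin.

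| Baseline grade | INR/PTT: baseline + 3 | Grades that trigger | Grade at a rise of exactly 2 | Transaminase/bilirubin: grades that trigger |
|---|---|---|---|---|
| 0 | 3 | 3, 4 | 2 | 2, 3, 4 |
| 1 | 4 | 4 only | 3 | 3, 4 |
| 2 | 5 | none | 4 | 4 |
| 3 | 6 | none | none | none |
| 4 | 7 | none | none | none |

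**Sensitivity to the ceiling.** If Grade 5 (death) is counted, baseline 2 triggers only at death, which changes nothing in practice. If the INR/PTT rows stopped at Grade 3, baseline 0 would trigger at Grade 3 and no abnormal baseline could ever trigger.

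**The exactly-2 branch.** A participant going from Grade 1 to Grade 3, or from Grade 2 to Grade 4, has risen by 2 and falls here. The Day 28 and Week 8 coagulation tests that the branch adds are already scheduled for every participant (C 1.2, C 9.4.7, C 9.4.8). What it really adds is the bleeding questions.

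**The resume clause.** A participant with baseline Grade 1 who is paused at Grade 4 and repeats at Grade 3 is at 3 - 1 = 2 above baseline, and so may resume under the numeric rule.

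**Table 1.** The row needs more than 2 patients, that is at least 3, each with a verified rise of more than 2 grades. A participant with baseline Grade 2 or higher can never contribute, and one with baseline Grade 1 contributes only at Grade 4. By contrast, the QTc row of the same table has an absolute limit as an alternative to the relative one.

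**The case against.** The strongest reply is that the numeric bullet is not the whole protection. C 12.1 lets the investigator or medical monitor stop study drug for a severe laboratory abnormality or a suspected anticoagulant effect, whatever the baseline grade, and says that its list is not exhaustive. C 13.5.1.3 provides monthly unblinded DSMB safety review that includes selected laboratory measurements (SAP Section 8 commits only to meetings at least every 6 months). Table 1 prompts consideration of a pause rather than a pause. Pilot rises were almost all Grade 1, with no bleeding. The amendment history says the pause criteria were added on an FDA recommendation. Enrollment has ended (SAP Appendix A).

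All of that stands, and it rules out several stronger readings that a reader might infer:

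- *That C 12.1 contradicts itself.* It does not, strictly. A mandatory trigger beneath a wider discretionary power is layered, and the exactly-2 branch is silent on dosing rather than directing it to continue. The guidance for a Grade 3 value reached from Grade 1 is unclear, not contradictory.
- *That a baseline Grade 1 participant must reach a life-threatening value.* The only life-threatening label in the documents is on the SAP's general scale, which describes symptoms and function and does not govern these tests.
- *That many participants cannot trigger at all.* No baseline of Grade 2 or higher is documented. The pilot statement speaks of mild abnormality, and the pilot graded increases by CTCAE v5.0, not DAIDS.
- *That the number affected can be stated.* The share with an abnormal baseline is not given. An assumed 20% to 40% of the planned 150 active participants would be 30 to 60, but enrollment ended before the interim trigger of 75 on upamostat completing Day 28. The same assumed share of 75 would be 15 to 30. Neither range is an estimate.

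What the reply does not do is make the numeric trigger, or the Table 1 count, reachable for participants who start with an abnormal value.

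**Conclusion.** The point holds as a defect in a stated rule. The mandatory trigger moves from Grade 3 to Grade 4 when the baseline moves from 0 to 1, and is out of reach from baseline 2 upward; Table 1 inherits the same gap. The baseline 1 case is the one that matters in practice, because mild baseline abnormality was common in the pilot and nothing in this appendix keeps such participants out.

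This rests on two things the documents do not show: that the DAIDS INR/PTT rows stop at Grade 4 (a lower ceiling would make the point stronger), and that the Master Protocol sets no INR/PTT entry limit (a limit would narrow it). The conclusion concerns the numeric rule and the study-level count. It is not a finding that participants were left without protection or that harm occurred.

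**What to change.** **Protocol.** Reconcile four places: the INR/PTT branches in C 12.1, the discretionary wording that opens C 12.1, the coagulation row of Table 1, and the baseline statement in C 3.4.1.1. The result should make clear how the trigger and the Table 1 count work for a participant whose baseline INR or PTT is already abnormal, and how the exactly-2 branch relates to the discretion to stop. The choice of threshold belongs to the sponsor, medical monitor and DSMB; none is proposed here. With enrollment ended, this matters for any further use of the appendix.

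**SAP 5.2.8.** Add a shift table of baseline DAIDS grade against worst on-study grade for INR and for aPTT, by arm, and counts of participants meeting the C 12.1 and Table 1 criteria by baseline grade. This applies to the present trial.

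**Cost.** A short amendment to C 12.1 and Table 1, with possibly a few more pauses in future use, and one extra table. No new test or visit is needed, since coagulation is already drawn at Day 0, Day 3, Day 14, Day 28 and Week 8.

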Transmembrane serine proteases are essential for viral fusion with the host cell membrane [Yao 2022]. Upamostat is a first-in-class orally administered potent inhibitor of serine proteases targeting multiple indications. Upamostat was initially studied as an inhibitor of urokinase plasminogen activator targeting oncology indications. Subsequent studies revealed that the compound is a potent inhibitor of other serine proteases, especially trypsins. The presumed mechanism is inhibition of spike protein cleavage necessary for viral entry into host cells. It targets human cell rather than viral factors and as such, is expected to be effective against emerging variants. In vitro, upamostat inhibited the original SARS-CoV-2 virus at a concentration well below that achievable in patients. Preliminary results of testing against SARS-CoV-2 BA.5 variant showed a 3-log decrease in viral titer at the highest dose tested. A pilot outpatient study in symptomatic, SARS-CoV-2 positive patients revealed that the drug was well tolerated at both dose levels tested, 200 and 400 mg daily for 14 days [Plasse 2022]. While the study was not powered for efficacy determination, only one of 41 patients (2.4%) receiving upamostat at either of the two doses used developed new severe symptoms on study, versus 4 of 20 (20%) of placebo recipients. Importantly, no upamostat-treated patient was hospitalized for COVID-19 during the study versus 3 of 20 (15%) of placebo recipients. Pharmacologic parameters (reduction in mean D-dimer levels and increased incidence of minor increases in INR and PTT) demonstrated dose-dependent effects.

C 3.3 Study Hypotheses

That early treatment with upamostat among outpatients infected with SARS-CoV-2 can shorten time to sustained symptom alleviation or resolution as compared to standard treatment.

C 3.4 Risk/Benefit Assessment

C 3.4.1 Known Potential Risks

C.3.4.1.1 Risks Associated with Upamostat

To date, 230 subjects have been treated with upamostat in clinical trials, including 41 in a recently concluded pilot study of upamostat for outpatient treatment of COVID-19.

In randomized clinical trials the only events attributable to upamostat were transient increases in transaminases, rash and, in patients receiving capecitabine, palmar-plantar erythrodysesthesia syndrome.

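### The liver row of the study-pause table says 'or' in its label but 'and' in its criterion, so read literally it never counts transaminase-only rises

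*Protocol*

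**What the plan says.** Section C 12.2 of Appendix C introduces Table 1 with "In addition to those listed in the Master Protocol, the study pause criteria listed in Table 1 will apply". The Master Protocol is not among the documents reviewed.

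The liver row has these parts:

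- **Label:** "ALT (SGPT), ALP (SGOT), or Total Bilirubin, High".
- **Criterion:** a verified abnormal rise of more than one grade in "AST, ALT, and total bilirubin in >2 patients". The column heading, which begins "Investigational Products Related Adverse Events (AEs", limits this to product-related events.
- **Footnotes:** c sets DAIDS grading. d defines a verified result as one repeated within 48 hours, with one exception: "When signs and symptoms are present, repeat test WILL NOT be needed".
- **Action:** report within 24 hours, consider pausing the arm, and have the PSRT watch for a trend.

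The coagulation row of the same table reads "> 2 Grade increase in verified PT, PTT or INR >2 patients", and its label also uses *or*. For the individual participant, C 12.1 says "Transaminases, bilirubin: increase over baseline >1 Grade above baseline: pause therapy".

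On the drug's known effects in randomized trials, C.3.4.1.1 says that "the only events attributable to upamostat were transient increases in transaminases", together with rash and, in patients on capecitabine, a palmar-plantar skin reaction. Bilirubin is not named.

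**The concern.** The two cells of one row give different rules. The label treats a rise in any listed analyte as the event. The criterion, taken word for word, needs AST, ALT and total bilirubin to have risen together in the same participant, in more than two participants. On that wording, rises confined to transaminases never count, however many participants have them.

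Transaminase rises are the hepatic effect that the protocol attributes to upamostat, so the literal criterion leaves out the pattern this row would most be expected to watch. At stake are the row's three actions: the 24-hour report, the pause consideration and the PSRT trend check.

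**Working it through.** The documents state no operating characteristic for this rule, so there is no figure to reproduce. The check compares the text and then counts under each reading.

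**1. Joining words side by side**

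| Place | Label | Criterion |
|---|---|---|
| Table 1, QTc row | single parameter | *or* |
| Table 1, liver row | *or* | *and* |
| Table 1, coagulation row | *or* | *or* |
| C 12.1, liver rule | – | comma only, no *and* |

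The liver row is the only one whose criterion uses *and*, and the only one whose two cells disagree. Footnotes c and d cover grading and verification, not this conflict. No other text in Appendix C or the SAP settles it expressly.

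**2. The second slip**

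SGOT is another name for AST, not ALP. The criterion cell names AST. The laboratory list in SAP 5.2.8 names aspartate aminotransferase and has no alkaline phosphatase. The label should therefore read AST (SGOT).

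**3. Counting patterns in one participant**

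Take every rise as product-related, verified and of more than one grade.

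- Non-empty patterns of {ALT, AST, bilirubin}: 2³ − 1 = 7. *Or* counts 7; *and* counts 1 (all three raised).
- Transaminase-only patterns: {ALT}, {AST}, {ALT, AST} = 3. *Or* counts 3; *and* counts 0.

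These counts follow from the two words alone. They are not probabilities, because the patterns are not equally likely and the documents give no rates.

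**4. Counting participants against the threshold**

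More than two patients means at least three. Suppose three participants each have an ALT-only rise. The same analyte is used in all three so that the result does not depend on whether different analytes may be pooled.

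- Under *or*: 3 > 2, so the row is met.
- Under *and*: 0 > 2 is false, so the row is not met.

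**5. What C 12.1 does in the same example**

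Its threshold is also more than one grade, so a rise found at Day 3 pauses that participant's dosing. Chemistry is next scheduled at Day 14, with blood drawn 22–26 hours after the previous dose. Dosing runs for 14 days from Day 0, so a rise first found then normally leaves no dosing to pause. C 12.1 therefore acts only where treatment is still under way, and it does not count across participants.

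**The case against.** The strongest reply is that *and* here simply lists the analytes being watched. The context supports this: the label, the coagulation row and the C 12.1 rule all point to *or*. That stands as to intent, and it is why the point concerns wording. It does not make the criterion safe as written, because a trigger that sites and the safety team apply should not need correcting by inference.

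The second reply is that little hangs on this row. Most of that stands too:

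- The row mandates no halt.
- C 12.1 pauses individuals, its list is not exhaustive, and it lets the investigator or medical monitor interrupt dosing for raised liver enzymes.
- The DSMB reviews unblinded safety data, monthly according to C 13.5.1.3 and at least every six months according to SAP section 8.
- The COVID-19 pilot saw no transaminase excess over placebo, though with only 20–21 patients per group.
- SAP 5.2.8 summarizes change from baseline in ALT, AST and bilirubin by arm, so hepatic effects will be reported whichever reading was used.

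None of these replaces the row's own 24-hour report, but together they keep the consequence small.

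A reader might go further and infer that a cluster of transaminase rises would have gone unnoticed, that a signal was missed, or that a three-analyte rule was chosen on purpose. The documents support none of these. The Master Protocol's pause criteria also apply and were not supplied, so whether another rule would have caught the same cluster cannot be judged. Nothing shows how the row was applied, and a protocol or SAP would not normally record that. Nothing suggests that a conjunctive rule was intended.

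**Conclusion.** The point holds as a drafting error in a safety trigger, and it is minor. Read literally, participants with product-related, verified rises of more than one grade in transaminases alone never count towards the liver row. Three such participants meet the row under the evident intent and contribute nothing under the printed wording. This rests on the text alone and needs no assumed event rate.

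The conclusion is confined to this row and its three actions. It says nothing about the adequacy of liver monitoring as a whole. SAP Appendix A records that enrollment ended before the interim trigger, and treatment lasts 14 days, so rewording the table now mainly corrects the record and any later use of the text.

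**What to change.** **Text.** In any amendment or reuse of Appendix C, change the criterion to a verified rise of more than one grade in AST, ALT, *or* total bilirubin in more than two patients. Keep the product-related condition in the column heading, and correct the label to AST (SGOT). The cost is one word and one abbreviation.

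**Clinical study report.** State which reading was applied during the trial. Then, as far as the captured data allow, report whether the *or* criterion would have been met and, if so, whether the 24-hour report and the pause consideration took place. The check needs three items:

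- DAIDS grade change from baseline, derived from the laboratory values. The listings planned in SAP 5.2.8 flag only values outside normal ranges, and abnormalities become graded adverse events only if considered clinically significant.
- Verification under footnote d: a repeat test within 48 hours, or signs and symptoms present. The documents do not show that this is held as analyzable data, so the check may be only partial.
- Causality from the adverse event listings, counting definitely, probably or possibly related, as in SAP 5.2.6.

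The laboratory and adverse event listings are already planned, so the added work is deriving grade change and joining the sources. No participant procedure is involved. If verification status cannot be recovered, say so and report the result without it.
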